5.6.1. PASI Assessments

Efficacy parameters related to the PASI score are defined below:

Time to regain disease control after start of re-treatment

The time to regain disease control is defined as time from the R0 visit (planned start of re-treatment) to first date PASI is <3 within the Re-treatment phase. In the absence of documented disease control the time to regain disease control will be censored at the date of the last PASI assessment until the week R24 visit. The time to regain disease control will be computed as:

- Date of PASI <3 – Date of week R0, if the subject regains disease control,
- Date of last PASI assessment – Date of week R0, if the subject does not regain disease control.

The following endpoints will be evaluated:

- Time to regain disease control (PASI <3) after start of re-treatment

The time to regain disease control will be analyzed using the Kaplan-Meier product limit method. Summary tables will provide counts and percentages by analysis group and overall, the median time-to-event with 95% CIs. The analysis will be performed on the observed cases only after the rule for handling of protocol-prohibited medication/therapy is applied. (ie, missing data will not be replaced for time-to-event analyses). Time to regain disease control will also be computed for subgroups (for the total only of analysis groups III to V), and subgroups will be compared using the log-rank test. The survival curves will also be displayed graphically: by analysis group and by subgroups.

Update after the Dry Run Meeting for the first interim analysis: The Kaplan-Meier analysis will not be performed on observed cases but as NRI analysis as PASI values under prohibited medication will not be used for analysis.

Update before start of programming for the final week 220 analysis: To harmonize with the statistical analysis for the Withdrawal phase, the Kaplan-Meier analysis will be performed on observed cases (OC) while PASI values under prohibited medication will not be used for analysis.

- Proportion of subjects who achieve a PASI value =0 over time
- Proportion of subjects who achieve a PASI value ≤ 1 over time
- Proportion of subjects who achieve a PASI value <3 over time
- Proportion of subjects who achieve a PASI value ≤ 5 over time

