5.5.1. Definition of Endpoint(s)

5.5.1.1. Psoriasis Area and Severity Index (PASI)

Efficacy endpoints related to the PASI score are defined below:

PASI 75 Responder

Subjects with $\geq 75\%$ improvement in PASI from baseline will be considered PASI 75 responders.

PASI 90 Responder

Subjects with $\geq 90\%$ improvement in PASI from baseline will be considered PASI 90 responders.

PASI 100 Responder

Subjects with a PASI score of 0 will be considered PASI 100 responders.

Time to loss of disease control

The time to loss of disease control is defined as time from the week 68 visit (start of withdrawal phase) to first date PASI is >5 within Study Part 3. In the absence of documented disease control, the time to loss of disease control will be censored at the date of the last PASI assessment until the week 116/164/220 visit. The time to loss of disease control will be computed as:

- Date of PASI >5 – Date of week 68, if the subject loses disease control,
- Date of last PASI assessment – Date of week 68, if the subject maintains disease control.
- In case the subject missed the week 68 visit, the start date of the withdrawal phase will be estimated as 8 weeks (56 days) after the week 60 visit.

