5.5.3. Analysis Methods

5.5.3.1. Psoriasis Area and Severity Index (PASI)

- Proportion of subjects who achieve a PASI 75/90/100 response at weeks 116, 164, and 220

The proportion of subjects still meeting the response criteria will be displayed in frequency tables providing the number and percentage of subjects per study group (NRI and OC analysis) along with odds ratio (OR), relative risk (RR) and risk difference (RD), and two-sided Wald-type 95% confidence intervals (95% CIs) stratified by 'disease duration'. For single proportions within each study group, unstratified two-sided 95% CIs according to Clopper-Pearson will be calculated. Graphical presentation will be presented by means of bar charts.

The two-group large-sample normal approximation Wald Z-test with Mantel-Haenszel stratum weights for 'disease duration' will be used to compare the proportion of responding subjects among the study groups. The Mantel-Haenszel estimate, the two-sided Wald-type 95% confidence limits, and the test for the difference of proportions will be computed by using Mantel-Haenszel stratum weights (Mantel & Haenszel, 1959) and the Sato variance estimator (Sato 1989).

Results will also be given for the entire population. In addition, in a modified OC analysis all subjects fulfilling the criteria for re-treatment within the week 116 visit window (ie, PASI>5) will be disregarded.

- Time to loss of disease control after treatment withdrawal beyond week 68

Time-to-event endpoints will be analyzed using the Kaplan-Meier product limit method and Cox proportional hazards model. Summary tables will provide counts and percentages by study group, the median time-to-event with 95% confidence intervals (CI), and the hazard ratio (including 95% CI and the p-value calculated from Cox-regression with the factors 'study group' and 'disease duration'). The survival curves will also be displayed graphically. Time-to-event analyses of binary endpoints will be performed on the observed cases only after the rule for handling of protocol-prohibited medication/therapy is applied. (ie, missing data will not be replaced for time-to-event analyses).

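### Time to regain control in re-treatment: the Kaplan-Meier median and its confidence interval mainly reflect the R8/R16/R24 visit calendar, not the speed of response

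*SAP*

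**What the plan says.** In the SAP for the re-treatment phase, section 5.6.1, the event time runs from the R0 visit "to first date PASI is <3 within the Re-treatment phase" and is computed as "Date of PASI <3 – Date of week R0, if the subject regains disease control". Subjects without documented control are "censored at the date of the last PASI assessment until the week R24 visit". The method is then fixed: "The time to regain disease control will be analyzed using the Kaplan-Meier product limit method". The output includes "the median time-to-event with 95% CIs" by analysis group and overall. For the total of analysis groups III to V, "subgroups will be compared using the log-rank test". Two dated updates in that section switch the analysis between observed cases and non-responder imputation and back. Neither addresses what happens between visits, and none of the documents mentions interval censoring.

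The protocol's re-treatment schedule places PASI at R0, R8, R16 and R24, with visits within ±7 days. Section 5.1.1 of the same SAP keeps unscheduled visits out of the summaries but lets them count towards clinically important endpoints.

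The SAP for Study Part 3 uses the same construction for time to loss of disease control. Section 5.5.1.1 defines it as "time from the week 68 visit (start of withdrawal phase) to first date PASI is >5 within Study Part 3", and section 5.5.3.1 says: "Time-to-event endpoints will be analyzed using the Kaplan-Meier product limit method and Cox proportional hazards model". On-site visits there are 12 weeks apart. A telephone call falls between them and leads to an on-site visit within 2 weeks if the subject reports worsening.

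**The concern.** What is known about a subject is that control was absent at one visit and present at the next. The event lies somewhere in an interval of about 8 weeks, and the plan always takes its right end. Kaplan-Meier then treats that date as exact. The median is pushed towards a visit date, and its confidence interval describes the scatter of appointment dates around that visit. It carries nothing about where in the interval the event fell.

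At stake is how the number is read. A median time to regain control of a little over 8 weeks, with a confidence interval a few days wide, would look like a precise measure of how fast guselkumab recaptures response. It would look nearly the same if half the subjects had regained control by week 2 or by week 6.

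**Working it through.** The documents give no expected median, event count or power for this endpoint, so there is no planned figure to reproduce. The check applies the SAP rule to simulated data.

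**Inputs from the documents**
- N = 227 subjects re-treated after the withdrawal phase (overall safety SAP, section 4.5).
- PASI after R0 at weeks 8, 16 and 24 (protocol, re-treatment schedule), ±7 days.
- Event time = date of first visit with PASI <3 minus date of R0; otherwise censored at the last PASI up to R24.

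**Assumptions not in the documents**
- Exponential true times with median m weeks.
- 5% early dropout.
- No unscheduled PASI.
- 300 runs per value of m.

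**Step 1: where the median lands.** With true time T and visits V1 < V2 < V3, the recorded time is the smallest Vj that is at least T. The proportion controlled by week 8 is 1 − 2^(−8/m). Whenever this exceeds one half, that is for m < 8, the Kaplan-Meier curve is expected to cross 50% at the R8 visit. With visits exactly on schedule, the simulated median was 8.00 weeks for every m from 1 to 6.

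**Step 2: with ±7 days of visit scatter**

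| True median (weeks) | Mean reported median | 2.5–97.5 percentile of runs |
|---|---|---|
| 1 | 8.01 | 7.86–8.14 |
| 2 | 8.08 | 8.00–8.29 |
| 3 | 8.23 | 8.14–8.43 |
| 4 | 8.38 | 8.14–8.57 |
| 6 | 8.72 | 8.50–8.86 |
| 7 | 9.37 | 8.71–15.00 |
| 8 | 11.90 | 8.86–15.57 |
| 10 | 15.52 | 15.14–16.22 |

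At 7 weeks most runs still give just under 9 weeks, but some jump towards R16, which lifts the mean. As the true median approaches 8 weeks, the reported value becomes unstable between R8 and R16.

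**Step 3: the confidence interval.** At a true median of 3 weeks the average 95% interval was 8.06 to 8.36 weeks. For true medians of 2 to 7 weeks it contained the true value in 0 of 300 runs.

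**Step 4: the subgroup test.** Take true medians of 3 and 6 weeks. The proportions controlled by week 8 are 1 − 2^(−8/3) = 84% and 1 − 2^(−8/6) = 60%, a gap of 24 points that is visible at R8. With about 113 subjects per subgroup, the log-rank test had 99.7% power. For 3 against 4.5 weeks it had about 68%, against about 88% if times were observed exactly. With no true difference it rejected in about 4% of runs.

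**Step 5: Study Part 3.** A true median time to loss of control of 30 weeks came out at about 33 to 36 weeks, depending on how often a telephone call leads to a visit.

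**The case against.** The strongest reply is that this is only a matter of labelling. The definition already refers to documented control, and the protocol defines loss of control as PASI >5 at a visit. The visit date also has meaning of its own in Study Part 3, because re-treatment starts then. Section 5.6.1 already tabulates the proportion with PASI <3 at each visit. The protocol's own re-treatment endpoint is the proportion at R24, reported with Clopper-Pearson intervals. Time to regain control was added in the SAP, and the whole analysis is exploratory.

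Most of this stands, and it limits the priority. It does not rescue the planned median and its interval: the by-visit proportions use non-responder imputation and carry no intervals, so nothing in the output tells the reader that the median is known only to within about 8 weeks.

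A reader might also infer that real subgroup differences in the first 8 weeks are lost. That holds for the printed medians only. Subgroups are compared by log-rank on a shared schedule, and Step 4 shows that the test keeps its error rate and most of its power.

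A further fair objection concerns a parametric remedy. An exponential interval-censored fit recovered a true median of 4 weeks as 3.98, but only because the data were generated as exponential. With log-normal times and a true median of 4.0, a Weibull fit averaged 3.1. With a 3-week lag followed by exponential times and a true median of 5.0, it averaged 4.3. Below week 8 the answer comes from the assumed shape.

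**Conclusion.** The point holds for the median and its confidence interval. If at least half the subjects have regained control by R8, the reported median will be about 8 to 9 weeks whatever the true value, with an interval that excludes the truth. The exact figures depend on exponential times, 5% dropout and no unscheduled PASI. The clustering at the visits follows from the schedule itself, although unscheduled assessments could supply some earlier dates.

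It does not extend to the log-rank comparisons, which remain valid with some loss of power for small differences, or to the R24 proportion. A reader might assume that Study Part 3 is equally affected. The documents do not support that: the telephone calls can shorten the intervals between PASI assessments, and the shift of about 3 to 6 weeks on a median of 30 is modest. Priority: minor.

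**What to change.** In section 5.6.1 of the re-treatment SAP:
- Label the Kaplan-Meier result 'time to first visit with documented control'.
- Add a nonparametric interval-censored (Turnbull) estimate, using the last visit without and the first visit with PASI <3. Give the median as the interval it falls in, for example 'above 0, up to 8 weeks'.
- Print the cumulative proportion controlled by R8, R16 and R24 with confidence intervals beside it.
- Keep the log-rank test.
- Do not present a parametric median below week 8 as a main result.

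In the Study Part 3 SAP, add the same interval-censored estimate as a sensitivity analysis for time to loss of disease control.

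No new data are needed. The cost is a little extra programming, less familiar output, and a bracket where readers may expect a single number.

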5.1.8. Missing Data Imputation

Data of efficacy endpoints from subjects who started a protocol-prohibited medication/therapy during the study that could improve psoriasis will be set to 'missing' from that point onward. If the prohibited medication was stopped and the stop date is before the R0 visit, any efficacy data observed on or after the R0 visit will be used for analysis. The protocol-prohibited medications/therapies are listed in section 8.1 of the CSP. For the statistical analysis of the Re-treatment phase, protocol prohibited medication/therapy will be identified in the SDTM DV domain as DVDECOD='Received a disallowed concomitant treatment'.

After the rule for handling of protocol-prohibited medication/therapy is applied, missing data will be handled as follows:

- Non-responder imputation for binary efficacy endpoints will be applied for subjects with missing data within a given visit window.
- Last Observation Carried Forward (LOCF) imputation for continuous efficacy endpoints will be applied for subjects with missing data in the Re-treatment phase. Only the visits R8, R16, and R24, or any unscheduled visit after R0, will be considered as the LOCF value.
 - This approach implies that a separate "endpoint" visit will be calculated that gets the imputed value, thus leaving the observed value as it is, if data are summarized descriptively only.
- Time-to-event analyses of binary endpoints will be performed after the rule for handling of protocol-prohibited medication/therapy is applied (missing data will not be replaced for time-to-event analyses).

An 'observed cases analysis' for all binary and continuous endpoints in the Re-treatment phase without any imputation of missing data (ie, also not set to missing once protocol-prohibited medication/therapy is started) will also be done. These analyses will provide only descriptive statistical results (see section 5.6).

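### The final analysis of time to regain control censors treatment failures as if they would regain like subjects still on re-treatment, so the curve can overstate regain by a few points

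*SAP*

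**What the plan says.** Re-treatment SAP 5.6.1 defines the event as the first PASI <3 after the R0 visit. For a subject without documented control, "the time to regain disease control will be censored at the date of the last PASI assessment until the week R24 visit". This sentence carries no update note.

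The same section then labels the Kaplan-Meier analysis in three ways:

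- Base text: "The analysis will be performed on the observed cases only after the rule for handling of protocol-prohibited medication/therapy is applied".
- As revised at the first interim stage: "The Kaplan-Meier analysis will not be performed on observed cases but as NRI analysis as PASI values under prohibited medication will not be used".
- Before programming for week 220, with harmonisation with the withdrawal phase as the only reason: "the Kaplan-Meier analysis will be performed on observed cases (OC) while PASI values under prohibited medication will not be used for analysis".

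Section 5.1.8 sets efficacy data to missing from the start of a prohibited therapy and adds that "missing data will not be replaced for time-to-event analyses". Section 5.1.6 defines no treatment failure criteria for this phase.

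Protocol 11.3 (Criteria for Endpoints) classes as treatment failures those who discontinue study agent for lack of efficacy, an adverse event or worsening, or who start a prohibited therapy that could improve psoriasis. It foresees applying treatment failure rules after week 68 in a separate analysis.

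Appendix 2 of the re-treatment SAP lists both label changes. The version 3.0 row of the version history does not mention the second.

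**The concern.** Kaplan-Meier censoring assumes that a censored subject would go on to have the event at the same rate as those still followed. Here the event is a success. A subject who starts another psoriasis therapy, or stops because the drug is not working, probably has a below-average chance of reaching PASI <3 on re-treatment. Censoring that subject gives them the success rate of those who remain.

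The planned subgroup tests also diverge. The R24 proportion follows the rule "Non-responder imputation for binary efficacy endpoints will be applied for subjects with missing data within a given visit window", and its subgroup chi-square test (5.5.3.1) uses NRI, so a failure-type exit without R24 data counts as a non-responder. The subgroup log-rank test in 5.6.1 censors the same subject. If failure-type exits are unevenly spread over subgroups, the two tests can differ for a reason that lies in the data handling.

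Harmonising with the withdrawal phase is a weak reason. The event there is loss of control, which is unfavourable, so the same censoring rule acts in a different direction.

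**Working it through.** The documents give no regain rate, median or drop-out for this endpoint, so there is no planned figure to reproduce. The calculation asks how far one minus Kaplan-Meier can lie above the cumulative incidence of regain.

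**Inputs from the overall safety SAP (4.1 to 4.5)**

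- Started re-treatment: 227 + 3 + 6 = 236.
- Part 2: 297 randomised subjects treated, 273 entered withdrawal, 9 were re-treated without withdrawal. Reaching neither: 297 − 273 − 9 = 15, or 15/297 = 5.1% over 40 weeks.
- Pro rata over 24 weeks: 5.1% × 24/40 = 3.0%, or about 7 of 236.
- A second reference: 58/880 = 6.6% did not start Part 2.

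Both are exits for any reason from other phases, so applying them to failure-type exits in re-treatment is an assumption and probably on the high side.

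**Assumed regain.** Conditional probability 0.60, 0.65 and 0.60 at R8, R16 and R24. Then 1 − KM at R24 = 1 − 0.40 × 0.35 × 0.40 = 94.4%.

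**Cumulative incidence, 7 exits without regain, one third (2.33) before each visit**

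- R8: (236 − 2.33) × 0.60 = 140.2 events, 93.5 left.
- R16: (93.5 − 2.33) × 0.65 = 59.2 events, 31.9 left.
- R24: (31.9 − 2.33) × 0.60 = 17.7 events.
- Total 217.2/236 = 92.0%. Gap 2.4 points, against a standard error of √(0.92 × 0.08/236) = 1.8 points.

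**Variations, same method**

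| Conditional regain | Exits without regain | 1 − KM | Cumulative incidence | Gap (points) |
|---|---|---|---|---|
| 0.60/0.65/0.60 | 7 (3%) | 94.4% | 92.0% | 2.4 |
| 0.60/0.65/0.60 | 12 (5%) | 94.4% | 90.3% | 4.1 |
| 0.50/0.60/0.50 | 7 (3%) | 90.0% | 87.8% | 2.2 |
| 0.50/0.60/0.50 | 5% | 90.0% | 86.3% | 3.7 |
| 0.25/0.30/0.238 | 5% | 60.0% | 57.8% | 2.2 |

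At 90% regain and 5% exits, timing moves the gap from 2.5 points (all after R16) to 4.5 (all before R8).

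**Bound.** Kaplan-Meier passes each censored subject's weight to those still at risk, and at most all of it becomes an event. The gap therefore cannot exceed the share of censored leavers.

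**Median.** In the first row, regain at R8 is 140.2/236 = 59.4% against 60.0%, so the median stays at R8.

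**Dependence on why subjects leave.** In a simulation with 90% regain in stayers and 5% prone to leave, truth is the regain had nobody left.

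| Leavers' chance per visit | Truth | OC Kaplan-Meier | All leavers held event-free |
|---|---|---|---|
| Same as stayers | 90.0% | 90.0% | 87.7% |
| Half | 88.6% | 89.7% | 86.8% |
| None | 85.6% | 89.2% | 85.6% |

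OC is unbiased in the first row and 3.6 points too high in the last.

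**The case against.** A reader might infer that the return to OC is what causes leavers to be censored, and that the interim NRI rule kept them event-free to R24. The documents do not show this. The censoring sentence stands under every label, and no section says how NRI treats a leaver in this analysis. The only reason given for the NRI label is that PASI under prohibited medication is not used, an exclusion that the OC wording also contains. Section 5.1.8 uses the OC label elsewhere for analyses that keep such values, so the change may be only a relabelling. For the same reason, one cannot assume that a suitable program exists from the interim.

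A reader might also infer that the curve overstates regain as a matter of fact. For ordinary loss to follow-up this is conditional: if leaving is unrelated to response, OC is unbiased and holding leavers event-free is too low.

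Nor does stopping drug end the chance of an event. Protocol 10.2 asks such subjects to attend scheduled visits for at least 12 weeks after the last dose, and a PASI <3 seen there counts under 5.6.1.

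The curve and the R24 proportion would differ in any case, because one records the first PASI <3 at any time and the other the status in the R24 window.

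Finally, the analysis is exploratory and was added by the SAP. PASI <3 over time is tabulated by NRI, and the R24 endpoint has NRI and OC results.

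These points narrow the issue and limit its weight. They do not remove it for failure-type exits, where the protocol itself names the exit a treatment failure and gives worsening psoriasis as an example of why prohibited medication is started (10.2).

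**Conclusion.** The point holds for failure-type exits: start of prohibited therapy, or discontinuation for lack of efficacy, worsening or an adverse event, without PASI <3. Censoring them is likely informative, and one minus Kaplan-Meier can then exceed the cumulative incidence of regain on re-treatment. The excess is bounded by their share and is about 2 to 4 points if that share is 3% to 5%. This rests on assumed regain rates and on drop-out borrowed from other phases; with few such exits it would be negligible.

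The unexplained OC, NRI, OC sequence is a separate defect of specification. As written, it is not possible to tell whether the interim and final curves follow one rule or two. The last change also came after the first interim re-treatment analysis.

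The change should be made, but it affects neither the confirmatory result nor the protocol-defined R24 endpoint.

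**What to change.** In re-treatment SAP 5.6.1:

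- Keep subjects who start prohibited therapy, or who discontinue for lack of efficacy, worsening or an adverse event, without PASI <3, event-free to the R24 target day (day 169). Apart from other censoring, this equals the cumulative incidence with these exits as competing events. Since R24 visits can fall after day 169, the Aalen-Johansen form is the safer way to program it.
- Still count any PASI <3 observed after study drug is stopped and before a prohibited therapy starts.
- Censor other loss to follow-up at the last PASI.
- Use the same handling for the subgroup comparison.
- Show the OC Kaplan-Meier curve next to it.
- State how leavers were handled under the NRI label at the first interim and whether the interim and final curves are comparable. Add the change to the version 3.0 row of the version history.

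The cost is SAP wording and minor programming, with reasons for exit taken from the discontinuation records. The downside is a slightly less favourable curve.
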